3. STATISTICAL METHODS

3.1 General

All data will be analyzed using the Statistical Analysis System (SAS®; Version 9.2 or higher).

Safety data will be summarized by study device group in summary tables. Continuous variables will be presented by descriptive statistics: n, mean, standard deviation (SD), median, minimum, and maximum, and categorical variables will be tabulated by frequency count and percentage.

3.2 Subject Disposition and Demographics

- Subject disposition will be summarized on ITT population by device group.
- Demographics will be summarized on ITT population by device group using descriptive statistics. Individual demographic data listing will also be provided.

3.3 Medical History and Concomitant Medications

- Individual data listings of general medical history and allergy history will be provided for the subjects of ITT population.
- Individual data listing of concomitant medication data will be provided for the subjects of ITT population. Subjects taken concomitant medication to treat AE/ADE will also be listed.

3.4 Adverse Events Analysis

AE rates will be summarized on ITT population by type of AE, occurrence rate, severity and device-relatedness, as defined below. The summary tables will document the event descriptions, the total number of events, and the number and the percentage of subjects affected in each device group to inform the Sponsor's product risk assessment.

All AEs will be coded using MedDRA. AE summaries will be presented by device group using the MedDRA level hierarchy (system organ class, high-level group term, high-level term, and preferred term) as follows:

- Overall (i.e., regardless of severity or relationship to treatment)
- By severity grade
- By relationship to study product according to the mapping scheme below:
 - Potentially related: will include all AEs with a relationship rating of "definitely", "probably" or "possibly".
 - Unlikely/not related: will include all AEs with a relationship rating of "unlikely" or "unrelated".

3.5 Device Deficiency Analysis

- Device deficiencies will be summarized on ITT population by type of deficiency and any relevant information about the deficiency. Individual device deficiency data will be provided.

3.6 Handling of Missing Data

For Safety data, missing data will not be imputed in general for Safety analysis. However, the below are some exception for conservative consideration.

- If the severity of an AE (ADE) is missing, then the AE (ADE) will be considered as "Severe".

- If the relationship to the study device of an AE is missing, then the AE will be considered as "Potentially Related" to study agent.

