2. BACKGROUND INFORMATION

2.1 Study Rationale

Between 2013 and 2016, an Irrimax-sponsored prospective clinical study entitled, “*A Phase IV, multicenter, prospective, randomized, controlled clinical study to compare the IrriSept system versus Standard of Care (SoC) on the prevalence of Surgical Site Infection (SSI) in patients with abdominal trauma or acute surgical abdomen*”, IRR-CT-901-2013-01, was conducted in the United States under IRB approval. A total of 19 sites were planned to participate in the study with only 17 sites enrolling subjects in the study, as listed above. A total of 625 subjects were consented and 600 subjects were randomized (1:1) and received irrigation either with Irrisept or the Standard of Care. Subjects were followed through study completion, and Protocol IRR-CT-901-2013-01 was previously closed with the IRBs. However, the Contract Research Organization and Sponsor’s executive management responsible

for undertaking this study during that period of time (2013-2016) were unable to complete the necessary monitoring activities and final data reporting.

In 2019, the Sponsor, under new management, intends to fulfill the Sponsor responsibilities by preparing a final study report for Protocol IRR-CT-901-2013-01. Upon recent review of the previously reported safety data from this closed study, the Sponsor determined that remonitoring of the subjects' source records is necessary to ensure complete and accurate reporting. Furthermore, an independent review of the device-related safety data by a Medical Monitor is needed.

Therefore, the Sponsor is initiating a retrospective review of the safety data, specifically all adverse events (AEs) and any device deficiencies that occurred in the closed clinical study based on the subjects' source records, including identifying any events or deficiencies that may not have been previously reported on case report forms (CRFs). The purpose of this retrospective review is to ensure all safety data on Irrisept are known and the product risk assessment documentation is current. All reported AEs will be assessed by an independent Medical Monitor. Device-related adverse events will be evaluated for any required reporting to regulatory authorities.

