5. STUDY POPULATION AND FOLLOW-UP

The study population, including inclusion and exclusion criteria, was defined in the closed study Protocol IRR-CT-901-2013-01. The closed study protocol allowed for enrollment of up to 1,100 subjects. At the 17 sites who enrolled subjects in the closed study, 625 subjects were consented, 600 subjects were randomized and received irrigation with either Irrisept or the Standard of Care, and 450 subjects completed the study. The study duration and follow-up schedule were previously defined in the closed study protocol. The closed study involved two visits: Visit 1 included screening, peri-operative and post-surgical; and Visit 2 was 30 days post-procedure.

This retrospective review will include all 625 previously consented subjects from Protocol IRR-CT-901-2013-01. The review will assess for documentation of informed consent for these subjects, and the subjects' source medical records will be reviewed for potential adverse events. There is no new subject enrollment or follow-up as part of this retrospective review.

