9.3 Source Documents

The Investigator must permit authorized representatives of the Sponsor and the IRB/EC to inspect facilities and original records relevant to this study. The study documents must be made available at reasonable times for inspection and duplication, if required, by a properly authorized representative of the U.S. FDA or other local or foreign regulatory authorities in accordance with regulatory requirements. The clinical monitors or auditors will check the eCRF entries against the source documents and inspect study files, subject medical records and other related study documents as required. These personnel will not disclose any protected health information.

As described in the ICH GCP Guidelines and ISO 14155, 'essential documents', including eCRFs, source documents, previously collected informed consent forms, laboratory test results, and device records, should be retained by the Investigator for at least 2 years or in accordance with institutional procedures. The Investigator must obtain written permission from the Sponsor prior to the destruction of any study document.

Investigators should maintain information in the study subject's medical records that corroborate data collected on the eCRFs. To comply with these regulatory requirements, the following information will be maintained:

- Medical history/physical condition of the study subject before involvement in the study sufficient to verify protocol entry criteria from the closed study protocol
- Dated and signed notes on the day of entry into the study including the study investigator, study name, subject number assigned and a statement that consent was obtained
- Information related to AEs and device deficiencies
- Discharge summaries/procedure reports

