1.2 Study Design

The closed study protocol allowed for enrollment of up to 1,100 subjects from 17 clinical sites. There were 625 subjects consented, where 600 subjects were randomized and received irrigation with either Irrisept system or the Standard of Care (SoC), and 450 subjects completed the study. The study duration and follow-up schedule in the closed study involved two visits: Visit 1 included screening, peri-operative and post-surgical; and Visit 2 was 30 days post-procedure.

This retrospective review will include all 625 previously consented subjects from the closed study. The review will assess for documentation of informed consent for these subjects. The subjects' source medical records will be reviewed for potential adverse events. There is no new subject enrollment or follow-up as part of this retrospective review.

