3.8 Key Data Items

Study Analysis Population Definition:

- Intended-To-Treat (ITT) population: All subjects who consented into the study and were randomized to use either irrigation product (Irrisept or SoC).

Important Derived Variables:

- Age = (Screening Date – Date of Birth +1)/365.25.
- Concomitant Medication and Treatments: The medications and treatments started after enrolled to the study (date of Informed Consent).
- Treatment emergent AE or ADE (TEAE/TEADE): Any AE (ADE) started on or after the day of using study device.

Formulas of Metric Conversion:

- 1 inch = 2.54 cm
- 1 lb = 0.4536 kg
- $^{\circ}\text{C} = ({}^{\circ}\text{F} - 32) \times 5/9$

AE Severity

GRADE	DESCRIPTION
0	No AE (or within normal limits)
1	Mild; asymptomatic or mild symptoms; clinical or diagnostic observations only; intervention not indicated
2	Moderate; minimal, local, or noninvasive intervention indicated; limiting age-appropriate instrumental activities of daily living (ADL)
3	Severe or medically significant but not immediately life-threatening; hospitalization or prolongation of hospitalization indicated; disabling; limiting self-care ADL
4	Life-threatening consequences; urgent intervention indicated
5	Death related to AE

AE Relationship to Study Device

By relationship to study product according to the mapping scheme below:

- Potentially related: including the ratings of "definitely", "probably" or "possibly"
- Unlikely related: including the ratings of "unlikely" or "unrelated"

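### AE percentages on the full ITT population cannot separate subjects with no event from subjects whose source record could not be fully reviewed, and the AE counting window has no stated end

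*SAP*

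**What the plan says.** - **Denominator.** SAP 3.4 summarizes AE rates on the ITT population, giving the number of events and "the number and the percentage of subjects affected in each device group". SAP 3.8 defines ITT by consent and randomization alone, with no condition on a usable record. The AE tables in SAP 4.1 all name the ITT population. The denominator is not written out, but no other population is defined.
- **Missing data.** SAP 3.6 states that "missing data will not be imputed in general for Safety analysis". It then gives two exceptions: a missing severity is treated as severe, and a missing relationship as potentially related.
- **Data collected.** For every subject, Protocol 9.1 lists whether AEs were identified in the source records. It lists no item for whether the source could be reviewed, or up to what date. Protocol 9.4 sends missing data to the sites as queries, with no rule for records that cannot be recovered.
- **Scope and follow-up.** SAP 1.2: "This retrospective review will include all 625 previously consented subjects from the closed study". Protocol 5: "600 subjects were randomized and received irrigation with either Irrisept or the Standard of Care, and 450 subjects completed the study". The last visit was 30 days after the procedure.
- **Window.** SAP 3.8 defines a treatment-emergent event as "Any AE (ADE) started on or after the day of using study device". This has a start and no end.

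**The concern.** The stated objective (Protocol 3, SAP 1.1) is that safety data be completely identified. The review looks back from 2019 at records of 2013 to 2016, for a study whose monitoring was not completed at the time (Protocol 2.1). In that setting, finding no AE can mean two things: the chart was read through Visit 2 and contained none, or there was little or nothing to read. The listed data do not tell these apart, and the ITT percentage treats them alike.

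At stake are the percentages that feed the product risk assessment. They may be too low by an amount the final report could not estimate. If record availability differed between the Irrisept and Standard of Care groups, part of that difference would show up as a difference in safety. A window without an end can act the other way: a long chart can contribute events after Day 30 that a short one cannot.

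**Working it through.** The plan states no AE rate, sample-size calculation, alpha or power, so there is no figure of its own to reproduce.

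**Step 1, counts from the documents** (Protocol 2.1 and 5, SAP 1.2)
- Consented but not randomized: 625 − 600 = 25. They are reviewed but lie outside the ITT population.
- Randomized but not completed: 600 − 450 = 150, and 150/600 = 25.0%.
- Protocol 2.1: "600 subjects were randomized (1:1) and received irrigation either with Irrisept or the Standard of Care". At 1:1 that is about 300 per group; actual group sizes are not given.

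**Step 2, what happens to an unreviewable subject.** The two exceptions in SAP 3.6 need an identified AE before they can act. A subject with no reviewable post-irrigation record has none, so contributes 0 to the numerator and 1 to the denominator. A subject with a partial record still counts as affected if an AE was recorded before the record ended.

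**Step 3, size as a function of assumptions.** Let p be the true 30-day subject-level AE risk, taken as equal in subjects with and without full records. Let u be the share of ITT with a lost or truncated record, and f the share of affected subjects among them whose AE is still captured. Then

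reported % = p × [1 − u(1 − f)]

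The documents give none of p, u or f. The multiplying factor is:

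| u (assumed) | f = 0 | f = 0.5 | f = 0.8 |
|---|---|---|---|
| 5% | 0.950 | 0.975 | 0.990 |
| 10% | 0.900 | 0.950 | 0.980 |
| 25% | 0.750 | 0.875 | 0.950 |

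With f = 1 the factor is 1.0 for any u, so u = 25% spans 0.75 to 1.0. At an assumed p of 20%, the u = 25% row gives 15.0%, 17.5% and 19.0%.

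**Step 4, what knowing the record status would add.** Take a group of 300 with 75 unreviewable subjects and 45 affected among the other 225 (assumed):
- all 75 counted as unaffected: 45/300 = 15.0%
- reviewable subjects only: 45/225 = 20.0%
- all 75 counted as affected: (45 + 75)/300 = 40.0%

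The middle figure equals the true risk only if missing records are unrelated to AE risk. Without a status field, only the first can be computed.

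**Step 5, unequal loss between groups.** Assume p = 20% in both groups, f = 0, and 150 unreviewable subjects split 60/90. Reported values are 20% × 240/300 = 16.0% and 20% × 210/300 = 14.0%. Split 50/100, they are 16.7% and 13.3%, an apparent ratio of 0.80 with no true difference.

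**The case against.** The strongest reply is that nothing in the documents shows a chart to be missing, and several provisions work against it.

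- **Lost charts.** A reader might infer from Protocol 9.3, where documents "should be retained by the Investigator for at least 2 years or in accordance with institutional procedures", that 2013–2016 charts were destroyed. The text does not support this. It is an instruction for the present review, it defers to institutional rules, and the next sentence forbids destruction without the Sponsor's written permission.
- **Non-completion.** That "450 subjects completed the study" says nothing about how many charts can be read. Non-completers may include deaths, which Protocol 7.2.2 requires to be recorded with the contributing event; such subjects count as affected.
- **A fixed understatement.** A reader might assume the 150 non-completers were observed for half the window on average and conclude that rates are 12.5% too low (1 − 0.875). The documents give neither the observed time nor the timing of events. Early events after an emergency laparotomy would be captured before a record ends.
- **No imputation.** A reader might take SAP 3.6 to rule out imputation altogether. It does not: it has two conservative rules.
- **Window.** The review covers AEs in the closed study, whose last visit was at 30 days, so an end is implied. The closed protocol, not available here, may state one. The planned table titles refer to AEs rather than treatment-emergent AEs, and onset time is tabulated in TAE07.
- **Form content.** Protocol 9.1 is a summary, so the eCRF or the separate Clinical Monitoring Plan may hold more. A disposition table and a discontinued-subject listing are planned.
- **Noise.** The analysis is descriptive. For 16.0% against 14.0% with 300 per group, the standard error is √(0.16 × 0.84/300 + 0.14 × 0.86/300) ≈ 2.9 points, more than the 2.0-point gap.

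All of this limits what may be claimed about size. It does not close the gap. Disposition is not linked to the AE denominators, and completion status does not show whether a chart could be reviewed. Queries do not settle what to do with an unrecoverable record, and an implied window is not a stated one.

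**Conclusion.** The point holds as a gap in what is recorded and reported, and it should be fixed. As written, the final report could not tell a subject without AEs from one who could not be assessed, which matters in a review whose purpose is completeness.

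The size is unknown. The factor of 0.75 to 1.0 rests on an assumed u of 25%, borrowed from the share of non-completers only for scale, and on equal AE risk in subjects with and without full records. The direction of any between-group bias cannot be determined. The net direction for a single group is also open, because late events counted without a cut-off would push its percentage up. That unreviewable subjects count as unaffected follows from the ITT definition and the absence of any other rule; the documents do not say it outright.

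**What to change.** 1. **eCRF (Protocol 9.1):** record for every subject the source status (full to Visit 2, partial, none) and the last reviewable date.
2. **SAP 3.2:** report both by device group, together with disposition.
3. **SAP 3.4 and 3.6:** write out the AE denominator. Keep the ITT percentages and add, as a sensitivity analysis, percentages among subjects with a reviewable post-irrigation record. This removes wholly missing records but not truncation, so event rates per person-day of reviewed record are a useful optional support.
4. **SAP 3.8 and the protocol:** state the AE counting window, consistent with the closed study's 30-day follow-up, and list later events separately so that none is discarded.

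Replacing the ITT denominator outright would be a trade-off and is not needed.

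**Cost:** two eCRF fields, some added tables, and possibly slightly higher stated AE rates. Every subject's source is to be reviewed anyway, so the fields are cheap if added beforehand. Protocol 9.1 says the eCRFs already exist; if the review is under way, filling them in means going back to as many as 625 subjects at 17 sites.

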4. OUTPUT PLANNED FOR THE STUDY REPORT

4.1 Tables to be Included in Study Report

4.1.1 *Summary of subject information*

1. Table [TDS01] Subject Disposition – ITT population
2. Table [TSC01] Summary of Surgical Procedure by Device Group – ITT Population
3. Table [TDM01] Summary of Demographics – ITT Population
4. Table [TDA01] Summary of Study Device Deficiencies – ITT Population

4.1.2 *Summary of AE*

5. Table [TAE01] Number (%) of Subjects with Adverse Events by MedDRA System Organ Class, High Level Group Term, High Level Term and Preferred Term – ITT Population
6. Table [TAE02] Number (%) of Subjects with Serious Adverse Events by MedDRA System Organ Class, High Level Group Term, High Level Term and Preferred Term – ITT Population
7. Table [TAE03a] Number (%) of Subjects with Adverse Events Grade 2 or Less by MedDRA System Organ Class, High Level Group Term, High Level Term and Preferred Term – ITT Population
8. Table [TAE03b] Number (%) of Subjects with Adverse Events Grade 3 or Higher by MedDRA System Organ Class, High Level Group Term, High Level Term and Preferred Term – ITT Population
9. Table [TAE04] Number (%) of Subjects with Adverse Events Potentially Related to Study Device by MedDRA System Organ Class, High Level Group Term, High Level Term and Preferred Term – ITT Population
10. Table [TAE05] Number (%) of Subjects with Adverse Events by Preferred Term and Overall Frequency – ITT Population
11. Table [TAE06] Number (%) of Subjects with Serious Adverse Events by SAE Criteria – ITT Population
12. Table [TAE07] Number (%) of Subjects with Adverse Events by Onset Time and Outcome – ITT Population
13. Table [TAE08] Number (%) of Subjects with Adverse Events by Severity and Relationship to Study Device – ITT Population
14. Table [TAE09] Number (%) of Subjects with Adverse Events by Action Taken and Irrisep Device Use Information – ITT Population

4.1.3 *Summary of ADE*

15. Table [TADE01] Number (%) of Subjects with Adverse Device Effects by MedDRA System Organ Class, High Level Group Term, High Level Term and Preferred Term – ITT Population
16. Table [TADE02] Number (%) of Subjects with Serious Adverse Device Effects by MedDRA System Organ Class, High Level Group Term, High Level Term and Preferred Term – ITT Population
17. Table [TADE03] Number (%) of Subjects with Unanticipated Serious Adverse Device Effects by MedDRA System Organ Class, High Level Group Term, High Level Term and Preferred Term – ITT Population

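### SAP 3.6 sets every missing AE severity to Severe (Grade 3), even when a fatal or life-threatening event is on record, so such an event would be under-graded in by-grade summaries

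*SAP*

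**What the plan says.** SAP 3.6 starts from a general rule that "missing data will not be imputed in general for Safety analysis" and then lists two exceptions, described as conservative:

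- Severity: "If the severity of an AE (ADE) is missing, then the AE (ADE) will be considered as" Severe.
- Relationship: "If the relationship to the study device of an AE is missing, then the AE will be considered as" Potentially Related.

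Neither exception refers to the outcome of the event. No rule is given for missing seriousness or for missing anticipated/unanticipated status.

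SAP 3.8 gives the severity scale. Grade 3 is "Severe or medically significant but not immediately life-threatening", Grade 4 is "Life-threatening consequences; urgent intervention indicated" and Grade 5 is "Death related to AE".

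SAP 3.4 promises AE summaries by severity grade. Among the outputs in SAP 4.1, TAE03a and TAE03b split at Grade 2 or less against Grade 3 or higher, and TAE08 crosses severity with relationship to the device. TAE06 is titled "Number (%) of Subjects with Serious Adverse Events by SAE Criteria".

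**The concern.** A conservative default should not place an event below what the rest of its record already shows. Under Protocol 9.1 the outcome of each AE is collected, and for serious events so are the SAE criterion met and any date and cause of death. Protocol 7.2.2 treats death as an outcome of the contributing event, so a fatal outcome attaches to a particular AE. If that AE has no severity entered, SAP 3.6 gives it a grade whose description contradicts its own outcome field.

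At stake is the top of the severity distribution in tables that are meant to inform the product risk assessment. Grades 4 and 5 would be undercounted and Grade 3 overcounted, and a reader would have no reason to suspect this under a rule described as conservative.

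**Working it through.** The plan gives no figure to reproduce. It is descriptive and states no AE count, missingness rate or event target. The check follows the rule through the scale and the planned outputs.

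**Step 1: which grade is Severe?** SAP 3.6 gives a word, not a number. In SAP 3.8 the word labels Grade 3 only. The mapping is inferred from that label, but it is the natural reading.

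**Step 2: size of the error per event.** Error = grade implied by the recorded outcome or criterion minus imputed grade.

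- AE with recorded death: 5 − 3 = 2 grades too low.
- AE with the life-threatening criterion recorded, not fatal: 4 − 3 = 1 grade too low.
- Any other AE: no recorded outcome or criterion places it above Grade 3, so the default contradicts nothing.

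**Step 3: which outputs change?**

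| Output | What places an event in it | Changed by Grade 3 instead of 4 or 5? |
|---|---|---|
| By-grade summaries (SAP 3.4) | individual grade | Yes, if single grades are shown |
| TAE08 | severity and relationship | Yes, if Grades 3, 4 and 5 are shown separately; only the title is given |
| TAE03a, TAE03b | Grade 2 or less / Grade 3 or higher | No; 3, 4 and 5 fall on the same side |
| LAE04a, LAE04b | Grade 3 or higher | No |
| TAE02, TAE06 | SAE status and criterion | No; SAP 2.2.1 defines an SAE by outcome, not grade |
| TAE07 | onset time and outcome | No |
| LAE06a, LAE06b | AE resulting in death | No |

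**Step 4: number of events.** Events under-graded = (fatal AEs with blank severity) + (non-fatal AEs with the life-threatening criterion recorded and blank severity). Neither count can be derived from the documents.

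**Step 5: seriousness and anticipated status.** SAP 3.6 has no exception for these fields, so a blank stays blank. TAE02, TAE06, TADE02 and TADE05 need seriousness, and TADE03 also needs unanticipated status. The SAP does not say how an event with either field blank is shown. Seriousness can be recovered in part from outcome under SAP 2.2.1. However, Protocol 9.1 collects SAE criteria and admission and discharge dates for serious events, so those items may be blank when seriousness is blank.

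**The case against.** The strongest reply is that the situation should hardly arise. Severity, relationship, seriousness and anticipated status are not just values recovered from old charts. Protocol 7.2.1 requires the Investigator to record all four for this review and the independent Medical Monitor to assess the same four for every AE. Protocol 9.1 puts each AE on a new, signed eCRF, Protocol 9.2 adds full source verification of AEs, and Protocol 9.4 sends missing items back to the sites. This stands as an argument about size. It does not remove the point: the SAP wrote a severity default for blanks that survive those steps, and for some of them the default contradicts recorded data.

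It is also fair to say that the rule does not overwrite a known grade, since it acts only when the grade is missing, and that the listed MedDRA tables by severity use a split the default cannot disturb. Both are accepted. If TAE08 also pools Grades 3 to 5 and no other by-grade table is produced, no count in the planned tables would change.

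A reader might go further and infer that these events drop out of the SAE and USADE tables. The documents do not support that. Blank severity removes nothing from the SAE tables, because death and threat to life are SAE criteria in their own right. Omission through blank seriousness or anticipated status would depend on how the tables are programmed, and the SAP is silent on it. Nor is a Grade 3 event counted as non-serious a contradiction in itself: Grade 3 also covers medically significant or disabling events, which need not meet an SAE criterion. Finally, regulatory reporting under Protocol 7.2.1 runs through the Medical Monitor's adjudication and the Sponsor's assessment, not through the table defaults in SAP 3.6.

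**Conclusion.** The point holds for the severity default. As written, SAP 3.6 under-grades a fatal AE with blank severity by two grades and a life-threatening one by one grade in any display by individual grade. The effect is confined to the SAP 3.4 by-grade summaries and to TAE08 if it separates grades.

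This rests on three assumptions: that Severe means Grade 3, that at least one output shows Grades 3, 4 and 5 separately, and that some severity fields remain blank after entry, adjudication and queries. The SAP also does not say whether the Investigator's or the Medical Monitor's rating feeds the tables, so it is unclear which blank triggers the rule. The total effect cannot be computed and is likely small.

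The absence of a rule for seriousness and anticipated status is a gap in detail. It calls for a clarification and does not show that events are lost.

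**What to change.** Amend the severity exception in SAP 3.6 along these lines: *missing severity takes the grade consistent with the recorded outcome or SAE criterion, namely Grade 5 if the AE resulted in death, Grade 4 if the life-threatening criterion is recorded and the AE was not fatal, and Grade 3 otherwise.* State the grade number, not only the word, and footnote each by-grade table with the number of imputed grades by device group.

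As a secondary clarification, add that blank seriousness is derived from the recorded outcome, SAE criteria and hospitalization dates under the SAP 2.2.1 definition. Any AE whose seriousness or anticipated status is still unresolved should then appear as a separate *not determined* count in the SAE and USADE tables. This avoids silent omission without labelling unassessed events as serious or unanticipated.

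The cost is a few sentences in SAP 3.6, one derived variable, a footnote and a possible extra row in the tables. The derivation uses only fields that Protocol 9.1 already collects. The severity change can only move an imputed grade up to match recorded data.
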